7.3.2.2 Cardiovascular Risk

Patients will be categorized into 1 of 3 coronary heart disease (CHD) risk subgroups based on National Cholesterol Education Program Adult Treatment Panel III Guidelines (NCEP ATP III) ([Grundy 2004](#); [NIH Publication No. 01-3670, 2001](#)). An algorithm will be used for assigning patients to a CV risk category (low, moderate, or high risk) in the lead-in studies.

A summary of adverse experiences will be provided for the CV risk factor subgroups listed above.

7.3.2.3 Clinical Laboratory Parameters

Descriptive statistics for clinical laboratory values (in SI units) and changes from the baseline values at each assessment timepoint will be presented by treatment group for clinical laboratory parameters. In addition, descriptive statistics for values and changes from the baseline values in conventional units at each assessment timepoint will be presented for selected clinical laboratory parameters. Patient narratives will also include the values in conventional units for the selected laboratory parameters.

Clinical laboratory test values will be considered potentially clinically significant (PCS) if they meet either the lower-limit or higher-limit PCS criteria. PCS criteria will be specified in the Statistical Analysis Plan (SAP). The number and percentage of patients who have PCS postbaseline clinical laboratory values will be tabulated by treatment group. The percentages will be calculated relative to the number of patients with available non-PCS baseline values and at least 1 postbaseline assessment. The numerator will be the total number of patients with available non PCS baseline values and at least 1 PCS postbaseline value. A supportive tabular display of patients with PCS postbaseline values will be provided, including the

patient number, baseline, and all postbaseline (including non-PCS) values. In addition, a tabular display showing all AEs that occurred in patients who had PCS postbaseline clinical laboratory values will be provided.

Shift tables from baseline to end of study for clinical laboratory parameters will be presented by treatment group for the following categories: low, normal, and high, which are provided by the lab vendor.

Any post-treatment ALT and/or AST results that are ≥ 3 times the ULN are considered events of clinical interest in this study and are subject to blinded adjudication by the Clinical Adjudication Committee to determine whether the elevation is due to treatment or not, and to determine whether there is a confounding factor. Patients with liver function laboratory findings that meet predetermined criteria will be summarized by treatment group along with the adjudication results. A detailed listing of all patients with any liver function laboratory findings will be provided.

7.3.2.4 Vital Sign Measurements

Descriptive statistics for vital sign measurements (sitting and standing systolic and diastolic BP, sitting and standing pulse rate, respiratory rate, temperature, weight, and BMI) and changes from baseline values at each visit and at the end of study will be presented by treatment group.

Vital sign values will be considered PCS if they meet both the observed-value criteria and the change-from-baseline criteria. PCS criteria will be specified in the SAP. The number and percentage of patients with PCS postbaseline values will be tabulated by treatment group. The percentages will be calculated relative to the number of patients with available non-PCS baseline values and at least 1 postbaseline assessment. The numerator will be the total number of patients with available non-PCS baseline values and at least 1 PCS postbaseline value. A supportive tabular display of patients with PCS postbaseline values will be provided, including the patient number, baseline and all postbaseline (including non-PCS) values.

In addition, a tabular display showing all AEs that occurred in patients who had PCS postbaseline vital sign values will be provided.

7.3.2.5 Electrocardiogram

Descriptive statistics for ECG parameters (heart rate, RR interval, PR interval, QRS interval, QT interval, and QTc) and changes from baseline values at each assessment timepoint to the end of study will be presented by treatment group.

Electrocardiographic parameter values are considered PCS if they meet or exceed the higher-limit PCS criteria. PCS criteria will be specified in the SAP. The number and percentage of patients with PCS postbaseline ECG values will be tabulated by treatment group. The percentages will be calculated relative to the number of patients with available non-PCS baseline values and at least 1 postbaseline assessment. The numerator is the total number of patients with available non-PCS baseline values and at least 1 PCS postbaseline value. A supportive tabular display of patients with PCS postbaseline values will be provided, including the patient number, baseline, all postbaseline (including non-PCS) values, and change from baseline. In addition, a tabular display showing all AEs that occurred in patients who had postbaseline PCS ECG values will be provided.

A shift table from baseline to the end of study in the investigator's overall interpretation of the ECG will be presented by treatment group for the following categories: normal, abnormal, not clinically significant, abnormal, clinically significant. A tabular display showing patients with postbaseline clinically significant ECG abnormalities according to the investigator's overall interpretation will be provided.

7.3.2.6 Suicidality Assessment

For the C-SSRS, the number of patients with suicidal ideation and suicidal behavior in lifetime history, during the treatment period, and during the Safety Follow-up period will be summarized by treatment group for the Safety population. Supportive tabular display of patients with all values will be provided, including patient number, treatment group, visit number, intensity of suicidal ideation, suicidal behavior type, and lethality of suicidal behavior.

7.3.2.7 Potential Hy's Law

Potential Hy's Law criteria within a 24-hour window is defined by a postbaseline elevation of alanine aminotransferase (ALT) or aspartate aminotransferase (AST) ≥ 3 times the ULN, along with total bilirubin (TBL) ≥ 2 times the ULN and a nonelevated alkaline phosphatase (ALP) < 2 times the ULN, all based on blood draws collected within a 24-hour period.

Potential Hy's Law criteria without time window (evaluation of drug-induced serious hepatotoxicity [eDISH]) is defined by maximum of postbaseline elevation of ALT or AST ≥ 3 times the ULN, along with maximum of postbaseline elevation of TBL ≥ 2 times the ULN.

Patients who meet the potential Hy's Law criteria from randomization to Visit 16 will be summarized. Supportive tabular displays also will be provided.

7.4 Subgroup Analyses

Subgroup analyses will be done for disposition, treatment exposure, and TEAEs for sex, age group (< 40 vs ≥ 40 , and < 65 vs ≥ 65), race (white vs all other races), cardiovascular risk category, and renal function class.

[REDACTED]

7.6 Interim Analyses

The interim analysis for Study UBR-MD-04 will occur when at least 300 ubrogepant patients (with a minimum of 2 migraines treated with ubrogepant per month, on average) have been enrolled in Study UBR-MD-04 for 6 months and 200 ubrogepant patients (with a minimum of 2 migraines treated with ubrogepant per month, on average) have been enrolled in Study UBR-MD-04 for 1 year.

In regards to blinding, although this is an open-label study, randomization to the ubrogepant 50 mg or 100 mg arms is blinded. If and when an interim analysis occurs, Allergan staff will be unblinded to the ubrogepant doses; however, patients and sites will remain blinded. The interim analysis will include all analyses specified in the SAP except for efficacy analyses.

Details regarding the interim analysis are specified in the SAP.

8. Study Visit Schedule and Procedures

Table 1 presents the schedule of visits and procedures.

8.1 Patient Entry Procedures

8.1.1 Overview of Entry Procedures

Prospective patients as defined by the inclusion and exclusion criteria in Sections 4.3 and 4.4 who completed Study UBR-MD-01 or UBR-MD-02 will be considered for entry into this study.

8.1.2 Informed Consent and Patient Privacy

The study will be discussed with the patient and a patient wishing to participate must give informed consent prior to any study-related procedures or change in treatment. The patient must also give authorization and other written documentation in accordance with local privacy requirements (where applicable) prior to any study-related procedures or change in treatment.

Each patient that provides informed consent will continue using the patient number assigned in the lead-in study for documentation throughout the study.

[REDACTED]

[REDACTED]

[REDACTED]

and [REDACTED]
[REDACTED]

[REDACTED] [REDACTED]
[REDACTED]
[REDACTED]

[REDACTED] [REDACTED]
[REDACTED]
[REDACTED]
[REDACTED]
[REDACTED]
[REDACTED]
[REDACTED]
[REDACTED]

- | [REDACTED]
- | [REDACTED]
- | [REDACTED]
- | [REDACTED] [REDACTED]
- | [REDACTED]
- | [REDACTED]
- | [REDACTED]
- | [REDACTED]
- | [REDACTED]
- | [REDACTED]
- | [REDACTED]
- | [REDACTED]

[Redacted]

- | [Redacted]
- | [Redacted]
- | [Redacted]
- | [Redacted]
- | [Redacted]
- | [Redacted]
- | [Redacted]
- | [Redacted]
- | [Redacted]
- | [Redacted]
- | [Redacted]
- | [Redacted]

[Redacted]

- | [Redacted]
- | [Redacted]
- | [Redacted]
- | [Redacted]
- | [Redacted]
- | [Redacted]

- [REDACTED]

[REDACTED]

[REDACTED]

[REDACTED]

[REDACTED]

- | [REDACTED]
- | [REDACTED]
- | [REDACTED]
- | [REDACTED]
- | [REDACTED]
- | [REDACTED]
- | [REDACTED]
- | [REDACTED]
- | [REDACTED]
- | [REDACTED]
- | [REDACTED]
- | [REDACTED]
- | [REDACTED]
- | [REDACTED]
- | [REDACTED]
- | [REDACTED]
- | [REDACTED]

[REDACTED]

[REDACTED]

[REDACTED]

- | [REDACTED]
- | [REDACTED]

- █ [REDACTED]
- █ [REDACTED]
- █ [REDACTED]
- █ [REDACTED]
- █ [REDACTED]

8.5 Instructions for the Patients

Section 4.5.3 provides diet and activity instructions for patients enrolled in the study.

All patients will be instructed to use an electronic diary (eDiary) to record details associated with their migraine attack. Training for the eDiary will be provided for qualified patients at Visit 2. Patients will be instructed to bring their eDiary to each clinic visit and for those who were dispensed ubrogepant, return their medication packs (used and unused).

8.6 Unscheduled Visits

Additional examinations and laboratory assessments may be performed as necessary to ensure the safety and well-being of the patients during the study period. Unscheduled visit eCRFs should be completed for each unscheduled visit. For all parameters not measured, indicate “not done”.

8.7 Compliance with Protocol

All assessments will be conducted at the appropriate visits as outlined in Table 1, and the timing of the visits should occur as close as possible to the specified day. At each visit, the patient will be asked if he or she changed the dose/regimen of any existing concomitant medications or initiated the use of any new concomitant medications since the last visit, to ensure compliance with the protocol.

Patients will record the requested information regarding their migraine attack and ubrogepant taken in the eDiary. Ubrogepant compliance will be closely monitored by counting the number of tablets dispensed and returned. Every effort will be made to collect all unused ubrogepant.

8.8 Early Discontinuation of Patients

A premature discontinuation will occur when a patient who signed the informed consent form (ICF) and was randomized ceases participation in the study, regardless of circumstances, before completion of the study. Patients can be prematurely discontinued from the study for 1 of the following reasons:

- AE
- Protocol violation
- Noncompliance with ubrogepant
- Withdrawal of consent (a clear reason must be documented)
- Lost to follow-up (every effort must be made to contact the patient; a certified/traceable letter must be sent)
- Lack of qualifying event (a qualifying migraine is not treated within 6 months)
- Pregnancy
- Other reasons

Patients may voluntarily withdraw from the study at any time. Notification of early patient discontinuation from the study and the reason for discontinuation will be made to Allergan and will be clearly documented on the appropriate eCRF. All randomized patients who prematurely discontinue from the study, regardless of cause, should be seen for a final assessment. A final assessment will be defined as completion of the evaluations scheduled for Visit 15/ ET. If the patient discontinues prematurely, the patient is expected to return for a Safety Follow-up visit 4 weeks after Visit 15/ET.

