5.6 Treatment Regimen and Dosing

5.6.1 Ubrogепant

Table 2 presents the treatments that will be administered in this study. Patients randomized to the ubrogепant arms will be instructed to take 2 tablets to treat their migraine attack regardless of the dose group to which they are assigned.

Table 2 Treatments Administered for Initial and Optional Second Dose

Drug/Dose	Dose Frequency	Route of Administration	Investigational Product Administered	
			Initial Dose	Optional Second Dose
Ubrogепant 50 mg	Up to 8 times/4 weeks for 1 year (with optional second dose – maximum 16 times/4 weeks)	Oral (tablet)	Ubrogепant 50 mg/ placebo 50 mg	Ubrogепant 50 mg/ placebo 50 mg
Ubrogепant 100 mg	Up to 8 times/4 weeks for 1 year (with optional second dose – maximum 16 times/4 weeks)	Oral (tablet)	Ubrogепant 50 mg/ ubrogепant 50 mg	Ubrogепant 50 mg/ ubrogепant 50 mg

Patients randomized to the ubrogепant arms will be allowed to treat up to 8 qualifying migraine headaches (of any pain severity) per 4-week period throughout the course of a year. Patients will be instructed to treat the migraine headaches as soon as possible when all of the following conditions are met:

- At least 48 hours since the last dose of ubrogепant
- At least 48 hours of pain freedom (ie, no headache for at least 48 hours)
- The migraine headache started less than 4 hours ago
- The migraine headache is not already resolving on its own
- Prohibited medication has not been taken

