5.6.2 Usual Care

Patients randomized to the usual-care arm will be instructed to treat their migraine with the medication(s) that they routinely take to relieve a migraine attack. Their usual medication(s) for acute treatment will be identified at Visit 1. At any time during the study, the patient's treating physician or the investigator may instruct these patients to change their migraine treatment. Any changes to the usual medication(s) identified at Visit 1 will be recorded in the

eCRF. There will be no limitations to the number of migraines treated and no qualifiers to treat a migraine for patients in this arm.

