7.1.2 Safety Population

The Safety population will be defined separately for the ubrogepant arms and the usual-care arm.

- Ubrogepant arms: All randomized patients who received ≥ 1 dose of treatment
- Usual-care arm: All randomized patients in the usual-care arm.

The purpose of the usual-care arm is to contextualize any safety findings that may occur in the ubrogepant treated patients over the course of 12 months. As such, data from all patients randomized to the usual-care arm, regardless of whether the patient used medication to treat migraine, will be included in the safety analyses.

[REDACTED]

[REDACTED]

[REDACTED]

[REDACTED]

[REDACTED]

[REDACTED]

[REDACTED]

[REDACTED]

[REDACTED]

[REDACTED]

[REDACTED]

- | [REDACTED]
- | [REDACTED]
- | [REDACTED]
- | [REDACTED]
- | [REDACTED]
- | [REDACTED]
- | [REDACTED]
- | [REDACTED]
- | [REDACTED]
- | [REDACTED]
- | [REDACTED]
- | [REDACTED]

[REDACTED]
[REDACTED]
[REDACTED]

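### The 6-month lack-of-qualifying-event reason in Protocol 8.8 can shorten safety follow-up on ubrogepant, with no defined equivalent in usual care

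*Protocol*

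**What the plan says.** Protocol 8.8 opens its list with "Patients can be prematurely discontinued from the study for 1 of the following reasons", and one of the reasons is "Lack of qualifying event (a qualifying migraine is not treated within 6 months". What ends is participation in the study, not only supply of drug. The patient is seen for Visit 15/ET and is expected at a Safety Follow-up visit 4 weeks later. No later follow-up is described.

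The word qualifying gets its content from 5.6.1, which concerns ubrogepant only: patients in the ubrogepant "arms will be allowed to treat up to 8 qualifying migraine headaches (of any pain severity) per 4-week period", subject to five conditions. One is "At least 48 hours of pain freedom (ie, no headache for at least 48 hours"; the others concern time since the last dose, time since onset, a headache already resolving, and prohibited medication. For usual care, 5.6.2 states: "There will be no limitations to the number of migraines treated and no qualifiers to treat a migraine for patients in this arm".

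The Safety population (Protocol 7.1.2, SAP Table 5-1) differs by arm. On ubrogepant it is "All randomized patients who received ≥ 1 dose of treatment". In usual care it is everyone randomized, and their data, "regardless of whether the patient used medication to treat migraine, will be included in the safety analyses".

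Adverse events are summarized as number and percentage of patients, from randomization to Visit 16, or to 30 days after the last visit or treatment, whichever is later, if there is no Visit 16 (Protocol 7.3.2 and 7.3.2.1, SAP Table 5-20).

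**The concern.** The usual-care arm is there to put one-year safety findings on ubrogepant into context. That works only if the arms are observed for comparable lengths of time. Section 8.8 contains a reason for ending observation whose key term is defined in two of the three randomized arms and expressly has no content in the third. Whether a patient meets it depends on how often that patient has and treats migraine, so the lost follow-up is not random.

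The visible analysis does not correct for this. A crude percentage treats a patient observed for 34 weeks like one observed for 56. The SAP does plan TEAEs by onset interval, but states no at-risk denominator for that table. Under the default denominator in SAP Table 5-2 (categorical descriptives), a discontinued patient still counts in later intervals in which nobody is watching. No rate per patient-year appears in the visible text. At stake is a modest downward shift in the ubrogepant percentages relative to usual care, in the direction that favours the drug.

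**Working it through.** The plan states no figure on this point, so there is none to reproduce. The check has two parts.

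**1. What the rule reaches.** There are two readings of the 6 months.

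- *First 6 months only.* A ubrogepant patient caught here has treated no qualifying migraine since entry. If no dose at all was taken, the patient is outside the Safety population, and removal changes no safety percentage.
- *Any 6-month gap.* A patient who has dosed and then lapses is in the Safety population and can lose the rest of the year. This is the only reading with a material effect on the safety tables.

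**2. Size under the second reading (illustration).**

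Inputs from the documents: 52 weeks of treatment plus 4 weeks of follow-up, so a completer is observed to week 56; 400 patients per arm.

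Assumptions, because the documents give no values:
- p, the proportion with the event by week 56;
- f, the share of the arm that lapses and is discontinued;
- a constant hazard, the same in lapsed and other patients;
- no matching loss in usual care.

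Formula: a lapsed patient observed to week w has expected proportion 1 − (1 − p)^(w/56). The arm's percentage falls by f × {p − [1 − (1 − p)^(w/56)]}.

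*Main case.* Last dose at week 4, gap complete at week 4 + 26 = 30, Safety Follow-up at week 34, p = 60%:
- 1 − 0.4^(34/56) = 0.427
- 0.600 − 0.427 = 0.173
- × 0.05, 0.10, 0.20 = 0.9, 1.7, 3.5 percentage points

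*Earliest case.* Dose at entry only, gap complete at week 26, observed to week 30, so 26 weeks (half a year) are lost:

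| p by week 56 | proportion by week 30 | fall at f = 5% | f = 10% | f = 20% |
|---|---|---|---|---|
| 50% | 31.0% | 0.95 | 1.90 | 3.80 |
| 10% | 5.49% | 0.23 | 0.45 | 0.90 |
| 2% | 1.08% | 0.05 | 0.09 | 0.18 |

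The last three columns are percentage points. The follow-up lost per arm is 400 × f × 0.5 = 10, 20 or 40 patient-years out of 400 × 56/52 = 430.8, that is 2.3%, 4.6% or 9.3%.

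*Scale.* With 400 per arm and 60% in each, the standard error of a difference between two arms is √(2 × 0.6 × 0.4/400) = 0.035, or 3.5 points. The main case is about a quarter, a half and one standard error at the three lapse shares.

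**The case against.** A reader might infer more than the text supports. Four stronger readings should be set aside.

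- *Usual-care patients are exempt and kept for the full year.* Nothing says so. Section 8.8 speaks of patients and names no arm. Usual-care patients also record attacks in the eDiary (Protocol 6.4 and 8.5), so a site could apply some version of the bullet to them. Section 7.1.2 settles whose data are analysed, not who is retained.
- *The rule removes low users.* One qualifying treated attack in each 6 months avoids it, and the wording is permissive, so removal is possible rather than automatic.
- *It removes patients whose headaches are too frequent for 48 pain-free hours.* They could meet it only if this, or another of the conditions, ruled out every attack for 6 months. How many such patients could be enrolled cannot be judged with most eligibility criteria redacted.
- *It distorts the Safety population.* Never-dosed ubrogepant patients are outside it already, by a separate definition.

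There is also a fair argument about consequence. The lost time follows 6 months without a treated qualifying attack, so the missed events would be mostly background events. The SAP will show discontinuation reasons by arm (Table 5-5) and numbers completing 3, 6, 9 and 12 months (Table 5-17), so an imbalance would be noticed. Redacted visit sections and parts of Section 7 may say more.

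Most of this stands and limits the point. It does not remove it. Usual care contributes background events for as long as its patients are followed, so losing them from the ubrogepant arms alone still tilts the comparison. Tables that reveal unequal follow-up do not adjust the percentages for it.

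**Conclusion.** The point holds in a limited form. Section 8.8 leaves both the arms and the 6-month window undefined, and its key term has meaning only for ubrogepant. Applied to any 6-month gap, it can cost a dosed ubrogepant patient up to about half a year of safety observation, and crude percentages would then run low in those arms.

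The effect is small for rare events (at most 0.18 points for a 2% event in the cases shown) and reaches a few points only for very common event categories combined with a large lapse share. These sizes rest wholly on the assumed event rates, lapse shares, constant hazard and absence of a similar loss in usual care. If lapsed patients have a lower hazard than the rest, the shortfall is smaller. If the rule means the first 6 months only, there is little or no effect on the safety tables. This is an inexpensive improvement to the comparison, not a flaw that undermines the study.

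**What to change.** In Protocol 8.8, remove lack of a qualifying event as a reason to end study participation. Patients who lapse then continue their scheduled safety visits through Visit 16, in line with the analysis window the SAP already uses. Whether drug continues to be dispensed to them is a separate matter for the sponsor, and nothing is proposed on it here.

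If the reason is kept:
- state one window (first 6 months, or any 6 months);
- apply one definition in all three arms, based on the eDiary attack record that every patient keeps;
- add to the SAP, by arm, total follow-up time and adverse events per patient-year beside the percentages.

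The cost of the main change is one bullet and some remaining safety visits for what is probably a small number of patients. The alternative costs a sentence or two in the protocol and a few added table columns.
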